## **9.2. Statistical Hypothesis**

The following hypotheses will be tested comparing the detachment rate of ADX-2191 (intravitreal methotrexate 0.8%) to that of a weighted historical control over 24 weeks.

- H0: There is no difference in rate of recurrent retinal detachment due to PVR between ADX-2191 (intravitreal methotrexate 0.8%) and historical control.
- H1: There is a difference in rate of recurrent retinal detachment due to PVR between ADX-2191 (intravitreal methotrexate 0.8%) and historical control.

## **9.3. Sample Size**

### **9.3.1. Sample Size Part 1**

The initial design of the GUARD Study was based on an recurrent retinal detachment rates of 0.2 and 0.5 for ADX-2191 and standard-of-care group, respectively. With a sample size of 90 subjects (45 per group) and 2-sided significant level at 0.05, the clinical trial would have approximately 80% power to detect the superiority of ADX-2191 over the standard-of-care.

The protocol was updated to an open-label, single arm study in Version 5.0.

Approximately 100 evaluable eyes will be recruited to complete the 24-week treatment period.

### **9.3.2. Sample Size Part 2**

The estimated rate of recurrent retinal detachment from Part 1 will be used to determinate sample sizes and power in Part 2, which is expected to require approximately 100-300 evaluable eyes (50-150 per treatment).

## **9.4. Statistical Analysis**

### **9.4.1. General Considerations**

Prior to database lock, the Sponsor will finalize a statistical analysis plan (SAP) detailing all planned analyses. Any analyses conducted in addition to those specified in the SAP will be clearly documented as post hoc. A summary of the currently planned analyses for the primary and secondary outcome variables is found below.

Quantitative variables will be summarized descriptively using number of subjects (n), mean, standard deviation, median, minimum, and maximum. Qualitative variables will be summarized using counts and percentages.

All summaries will be presented by treatment group. Summaries will be provided for demographics, baseline medical history, concurrent therapies, and subject disposition.

For the purpose of summarization, medical history, concurrent therapies, and adverse events will be coded to MedDRA and WHO Drug dictionaries, as appropriate.

All analyses will be two-sided at a significance level of 0.05. The 95% confidence intervals will be provided where appropriate.

The primary endpoint analysis will compare retinal detachment rates of drug-treated subjects to a historical control rate, which will be a weighted average of the retinal re-detachment rates from two prior Grade C PVR prospective clinical trials with similar inclusion criteria (Banerjee, 2017; Schiff, 2007).

The SAP will serve as the final determinant of the statistical procedures, notwithstanding language herein.

### **9.4.2. General Imputation Methods**

Every attempt will be made to capture all clinical trial data. The method on how to handle the complete and/or partial missing data in the adverse events and medications will be addressed in these individual analysis sections of the SAP. No imputation method will be applied on recurrent retinal detachment data.

### **9.4.3. Multiplicity Consideration**

Only one hypothesis will be tested. No multiplicity adjustment will be done in this clinical trial.

### **9.4.4. Demographic and Baseline Medical History**

The demographic and baseline medical history data, obtained at screening, will be summarized descriptively. For quantitative variables, the summaries will include the number of observations, mean, standard deviation, median, minimum, and maximum. Qualitative variables will be summarized using counts and percentages.

#### **9.4.5. Primary Efficacy Analyses**

The primary efficacy variable of recurrent of retinal detachments (defined in Section 3.6) due to PVR requiring re-operation within six months from enrollment will be measured as binary variable (indicating recurrent of detachment or not). Briefly, a 95% confidence interval around the proportion of retinal detachment in drug-treated subjects will be generated, and the primary endpoint will have been deemed to have been met if the upper bound of the confidence interval is lower than the weighted average historical control detachment rate. The primary efficacy analyses will be conducted on the ITT population with observed data only. Subjects who discontinue investigational treatment early will be encouraged to stay for any remaining safety assessments until the conclusion of the clinical trial. Subjects who have retinal detachment within 1-week post-operatively will be deemed to have failed Day 0 (day of surgery), and will be removed from the efficacy analysis.

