### **2.2. Clinical Trial Endpoints**

#### **2.2.1. Primary Endpoints**

The primary endpoint in Part 1 and Part 2 is recurrent retinal detachment requiring reoperation within 24 weeks from time of enrollment. An evaluating investigator should determine whether the primary endpoint has been met. The primary endpoint requires verification by the Central Reading Center (CRC) before recurrent retinal detachment reoperation. In cases where CRC verification is not possible due to technical limitations with the Optical Coherence Tomography or fundus photograph, then the evaluating investigator will contact the trial medical monitor to confirm whether the primary endpoint has been met. These verification processes provide an additional level of objectivity in end point evaluation.

Definition of recurrent retinal detachment (defined as either one OR both of the following):

1. Spectral-Domain Optical Coherence Tomography (SD-OCT) demonstrating fovea-off retinal detachment (subfoveal fluid that is contiguous with a peripheral detachment);
2. Color fundus photographic documentation of a rhegmatogenous or tractional (or undetermined) retinal detachment that has progressed posterior to the Mandatory Reoperation Zone, as defined as defined by a circle centered on the fovea, with a radius halfway between the arcades and the equator (Figure 2).

Stable, peripheral rhegmatogenous or tractional (or undetermined) detachments anterior to the mid-periphery may be observed or demarcated with laser at the investigator's discretion and will not be counted as failure.

Subjects who have retinal detachment within 1-week post-operatively will be deemed to have failed Day 0 (day of surgery) and will be removed from the efficacy analysis. These will be considered "dropped" subjects. Subjects receiving investigational product during this period will continue to be followed for safety. Retinal detachment is defined as subjects who meet either of the recurrent retinal detachment imaging criteria as defined in the Primary Endpoint.

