### **3.6. Clinical Trial Population Selection**

The intended population will be adult subjects undergoing pars plana vitrectomy for the following indications:

1. Recurrent retinal detachment due to PVR with documented starfolds in at least three cumulative clock hours on retinal imaging. (Imaging modality methods defined in Section 6.8.5).
2. Retinal detachment associated with open globe injury (the open globe retinal detachments may or may not have PVR at the time of enrollment).

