### **6.8.4. Endpoint Evaluation**

It is preferred that an evaluating investigator assess whether the primary endpoint has been met at the pre-specified evaluation timepoints Weeks 1 (V4), 4 (V7), 8 (V11), 12 (V13), 16 (V15), and 24 (V16). If an evaluating investigator is not available, the Treating Investigator may determine whether the primary endpoint has been met. The primary endpoint requires verification by the CRC before recurrent retinal detachment reoperation. In cases where CRC verification is not possible due to technical limitations with the Optical Coherence Tomography or fundus photograph, then the evaluating investigator will contact the trial medical monitor to confirm whether the primary endpoint has been met. Regardless, SD-OCT and wide-field imaging will be collected and verified by the CRC when the endpoint has been met, or at conclusion of the clinical trial, whichever is sooner.

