11. Silicone oil removal is required after Week 24.

Investigators will have discretion regarding the need for re-operation. Indications for re-operation may include endophthalmitis and recurrent retinal detachment, as defined in Section 3.6. Silicone oil cannot be removed within the 24-week trial period, unless for the above indications.

Recurrence of retinal detachment requiring a return to the operating room will prompt cessation of any further intravitreal injections and only Routine Surgical Care will be provided. Subjects will be followed through the Week 24 assessment visit.

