# **7. CLINICAL TRIAL ACTIVITIES**

Clinical trial activities are summarized in the Schedule of Events and Assessments (Table 1).

NOTE: Event weeks are defined as follows: post-operative Week One starts the calendar week following surgery (e.g., if Day One is Friday, Week One can start on Monday). Post-operative Week 24 must be at least 24 weeks from day of surgery  $\pm$  2 weeks.

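### The primary event is worded three ways, with and without a restriction to PVR-caused detachment and no rule for attributing cause; separately, the plan does not show that the Grade C PVR benchmark applies to the pooled open-globe eyes

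*Combined protocol and SAP*

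**What the plan says.** **The event.** Section 2.2.1 sets the primary endpoint as "recurrent retinal detachment requiring reoperation within 24 weeks from time of enrollment". The imaging definition is fovea-off detachment on SD-OCT or "Color fundus photographic documentation of a rhegmatogenous or tractional (or undetermined) retinal detachment that has progressed posterior to the Mandatory Reoperation Zone". No cause is required, and undetermined detachments count. The synopsis agrees.

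Section 9.2 states the null hypothesis as "There is no difference in rate of recurrent retinal detachment due to PVR between ADX-2191" and historical control, over 24 weeks. Section 9.4.5 describes the variable as "recurrent of retinal detachments (defined in Section 3.6) due to PVR requiring re-operation within six months from enrollment".

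Section 6.9 also sends the reader to Section 3.6, listing as indications for re-operation "endophthalmitis and recurrent retinal detachment, as defined in Section 3.6". Section 3.6 gives the population and the eligibility criteria.

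**Verification.** Section 6.8.4 says "The primary endpoint requires verification by the CRC before recurrent retinal detachment reoperation". The medical monitor confirms the endpoint when images are technically inadequate. Neither step mentions cause.

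**Population and benchmark.** Eyes qualify with recurrent detachment due to PVR (inclusion 2a) or with detachment after open-globe injury (2b), and Section 3.6 adds that "the open globe retinal detachments may or may not have PVR at the time of enrollment". Section 9.4.5 tests one proportion in drug-treated subjects. Success requires the upper 95% limit to fall below a weighted historical rate. Section 9.4.1 takes that rate from two Grade C PVR trials, described as having similar inclusion criteria. It gives no rate, weights or event definition.

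**The concern.** The trial has one hypothesis, one proportion and one fixed threshold, so anything that changes the numerator or the meaning of the threshold acts directly on the success claim.

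On the same eyes and window, restricting events to those caused by PVR can only leave the count unchanged or reduce it. If the historical rate counts all re-detachments, that favours the drug. If the historical rate counts only PVR-caused ones, the 2.2.1 count works against the drug. The documents do not settle which holds. The trial is open-label, and Section 6.8.4 lets the treating investigator judge the endpoint when no evaluating investigator is available, so an undefined cause judgement should not be left in the text.

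The threshold is also a fair null value only if untreated eyes of this mix would re-detach at that rate. The only support offered is the phrase about similar inclusion criteria. It is not shown for open-globe eyes, and the starfold criterion in 2a is not mapped to Grade C.

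**Working it through.** **1. The wordings side by side**

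| Place | Cause restriction | Window |
|---|---|---|
| Synopsis; 2.2.1 | none; undetermined detachments count | 24 weeks from enrollment |
| 9.2 hypotheses | due to PVR | 24 weeks |
| 9.4.5 variable | due to PVR | six months from enrollment |
| 9.4.5 coding and decision rule | none | not restated |
| 9.4.1 benchmark | none | not stated |
| 6.8.4 evaluation and verification | none | visits to Week 24 |

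The words any cause appear nowhere. That reading of 2.2.1 follows from the absence of a restriction and the inclusion of undetermined detachments.

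**2. Window.** 24 weeks = 24 × 7 = 168 days; six months = 365.25/2 ≈ 182.6 days. Section 7 says "Post-operative Week 24 must be at least 24 weeks from day of surgery", with a tolerance of two weeks, so the visit may fall as late as day 168 + 14 = 182. An event first seen on days 169 to 182 is inside six months and outside 24 weeks. No endpoint evaluation is scheduled later, so this gap is minor beside the cause restriction.

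**3. The plan's own sample size.** Section 9.3.1: rates 0.2 and 0.5, two-sided 0.05, 80% power.
- Uncorrected n per arm = [1.960√(2·0.35·0.65) + 0.842√(0.2·0.8 + 0.5·0.5)]² / 0.3² = 38.5, so 39.
- With continuity correction: (38.5/4)·[1 + √(1 + 4/(38.5·0.3))]² = 44.9, so 45 per arm.

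The stated 45 per group reproduces, but it belongs to the superseded two-arm design. No power is given for the single-arm rule.

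**4. What a cause filter could do.** Assumptions: benchmark T = 0.50 (the standard-of-care planning rate in 9.3.1), counted for all causes; exact (Clopper-Pearson) interval, since the method is not stated; inert drug; 100 or 50 treated eyes. The upper limit for x events is the 0.975 quantile of Beta(x+1, n−x).
- n = 100: 39 events give 0.493 and 40 give 0.503, so success needs at most 39.
- n = 50: 17 events give 0.488 and 18 give 0.508, so success needs at most 17.

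False success = P(X ≤ limit), X ~ Bin(n, T·f), where f is the assumed share of events called PVR-caused:

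| f | 100% | 95% | 90% | 85% | 80% |
|---|---|---|---|---|---|
| n = 100 | 1.8% | 5.4% | 13% | 27% | 46% |
| n = 50 | 1.6% | 3.7% | 7.7% | 14% | 24% |

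At f = 90% with T = 0.40 or 0.45, the figures are 13% and 11% (n = 100; limits 30 and 34), and about 5% and 8.4% (n = 50; limits 12 and 15).

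**5. What pooling could do.** Same rule and T = 0.50. Assume 20% open-globe eyes (2 of 10 in the Phase 1b study, Section 1.1) with untreated risk r. The pooled rate is 0.8·0.50 + 0.2·r.

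| r | 10% | 20% | 30% | 40% | 50% | 60% |
|---|---|---|---|---|---|---|
| n = 100 | 31% | 18% | 9.6% | 4.4% | 1.8% | 0.6% |
| n = 50 | 16% | 9.9% | 5.8% | 3.2% | 1.6% | 0.8% |

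Large inflation needs open-globe risk well below the benchmark; a higher risk makes the test stricter.

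**6. Power of a 2a-only comparison.** True rate 20%; 80 or 40 eyes (100 or 50 less the assumed 20%); power = P(Bin(n, 0.20) ≤ limit).

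| Threshold | n = 80 (limit) | n = 40 (limit) |
|---|---|---|
| 40% | 98% (23) | 73% (9) |
| 45% | above 99% (26) | 91% (11) |
| 50% | above 99% (30) | 98% (13) |

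**The case against.** The best defence is that the restriction is loose wording carried over from the objective in 2.1.1. After the disputed phrase, 9.4.5 codes the variable simply as detachment or not and puts the interval around the proportion with detachment. Nothing in 6.8.4 or 2.2.1 creates a cause step. That makes the imaging event the likelier count in practice. It does not remove the contradiction, because the hypotheses and the definition of the tested variable still carry the restriction.

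Section 9.2 also applies the PVR wording to both sides, so as worded the hypothesis is symmetric. But 9.4.1 and 9.4.5 describe the benchmark without that qualifier, so the sections point different ways.

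On pooling, both indications are named in the objective, so combining them is deliberate. Section 9.4.1 asserts similar inclusion criteria and nothing in the documents rebuts it. The SAP, to be finalized before database lock, overrides the protocol and could supply the benchmark and its justification. This stands, and it is why pooling is the lesser part.

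The illustrations are also open to challenge. No section supports any attribution share or any open-globe risk. The 20% share rests on ten eyes (exact 95% interval 3% to 56%). The 50% was planned for a trial enrolling both presentations, so using it as the rate for non-open-globe eyes in step 5 is questionable.

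A reader might infer that events will be filtered by cause and the error rate is therefore 13% or more, or that open-globe eyes make the test easier to pass. The documents support neither: the operative sentences point away from a filter, no open-globe rate is given, and Section 1.1 counts such eyes among those at high risk.

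**Conclusion.** **Must fix, high confidence:** the definition of the primary event is internally contradictory. This rests on the text alone: three wordings, no attribution rule, and a reference in 9.4.5 and 6.9 to a section that does not define the event. The window difference is a small part of it.

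**Should fix, lower confidence:** the applicability of a Grade C PVR rate to a pooled group that includes open-globe eyes is asserted and not shown. It is a gap in justification, not a demonstrated error, and neither the direction nor the size of any bias can be determined.

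The false-success figures show that the rule is sensitive to modest mismatches between what is counted and what the benchmark counts. They depend on the assumed benchmark, interval method, attribution shares and open-globe risks.

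**What to change.** **Event.**
- Remove the PVR restriction from the hypotheses in 9.2 and from 9.4.5. Use the verified 2.2.1 event within 24 weeks throughout, and state that an event first seen at the Week 24 visit within its window counts.
- Point 9.4.5 to 2.2.1. The Section 3.6 reference in 6.9 must be reconciled with 2.2.1. Section 2.1.1 can keep the phrase as the aim of treatment.
- In the SAP, give the benchmark value, state how each source trial counted re-detachment, and build the benchmark on the same all-cause count. If a source reports only PVR-caused events, say so and add a matching sensitivity count, with cause attributed by masked reading-center graders from images already collected.

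**Population.**
- Keep the pooled primary test. Add to 9.4.5 a pre-specified supportive analysis applying the historical comparison to inclusion-2a eyes only.
- Report the detachment rate with 95% interval by indication, alongside the Part 1a control rate by indication. State why the benchmark applies to each indication.

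**Cost.** This is protocol and SAP wording, plus some reading-center grading if the sensitivity count is needed. The 2a-only analysis has fewer eyes: with 40 eyes and a 40% threshold, a drug with a true 20% rate would miss about 27% of the time (100% − 73%), so a miss there is not by itself evidence against the drug. Open-globe intervals will be wide: 4 events in 20 eyes gives 6% to 44%.

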## SYNOPSIS

Name of Sponsor Company: Aldeyra Therapeutics, Inc.	Investigational Product: ADX-2191	
Title of Protocol: A multicenter, adaptive Phase 3 clinical trial of repeated intravitreal injections of ADX-2191 versus standard-of-care for the prevention of proliferative vitreoretinopathy		
Protocol Number: ADX-2191-PVR-001	Phase: 3	Indication: Prevention of Proliferative vitreoretinopathy
Subject Population: Adult subjects undergoing pars plana vitrectomy for the following indications: 

• Recurrent retinal detachment due to proliferative vitreoretinopathy (PVR) with documented starfolds in at least three cumulative clock hours on retinal imaging.

• Retinal detachment associated with open globe injury (OGI).

		
Number of Subjects: The trial will utilize an adaptive design with the number of subjects enrolled for Part 2 determined in Part 1. Part 1: Approximately 100-120 subjects will be enrolled to obtain approximately 100 evaluable eyes (50 subjects per treatment). Part 2: An additional 100-360 subjects will be enrolled to obtain approximately 100-300 evaluable eyes (50-150 subjects per treatment); to be statistically powered following completion of Part 1.		
Number of Centers: Approximately up to 30 sites in the United States		
Test Products / Dose / Mode of Administration: ADX-2191 (intravitreal methotrexate 0.8%) 400 mcg in 0.05 mL for 13 repeated intravitreal injections over 16 weeks		

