Overall Design: In Part 1a of the GUARD Study (prior to activation of Protocol Version 5.0, dated May 5 2021), eligible subjects will be randomized 1:1 intraoperatively to either the Control or Intervention cohort. Subjects in the Control cohort will receive Standard Procedures only. In Part 1b of the GUARD Study (after activation of Protocol Version 5.0, dated May 5 2021), eligible subjects will no longer be randomized and all enrolled subjects will be placed in the Intervention Cohort. Subjects in the Intervention cohort will receive Standard Procedures and intravitreal ADX-2191 injections (Figure 1). In Part 1a, stratification will be used to balance treatment assignments within key subgroups. Subjects are to be stratified by clinical presentation (recurrent retinal detachment vs. OGI) and number of recurrent retinal detachments (>3 vs. ≤3). Subjects enrolled in Part 1 will not be eligible to participate in Part 2 nor will they be eligible to be randomized again during Part 1. Clinical trial procedures to be conducted in Part 1 and Part 2 are outlined in the Schedule of Assessments (Table 1).		

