## 1. INTRODUCTION

### 1.1. Proliferative Vitreoretinopathy

Currently, proliferative vitreoretinopathy (PVR) is the leading cause of failure of rhegmatogenous retinal detachment surgery, resulting in recurrent retinal detachment in 5%–10% of all cases. (Pastor 2008) PVR is an abnormal wound healing response that involves the proliferation of ectopic cell sheets, in which cells grow uncontrollably within the vitreous cavity as well as beneath and/or on the surface of the retina resulting in periretinal membrane formation, retinal traction, and re-detachment. Despite tremendous advances in ophthalmic surgical instrumentation and techniques, anatomic success following recurrent detachment from PVR is reported to be only 45%–80%, depending on the severity of the cases (Banerjee, Bunce, & Charteris, 2013). Furthermore, functional success (visual acuity 5/200 or better) is achieved in only 40%–80% of subjects who achieve anatomic success.

The current standard-of-care for the treatment of PVR is vitreoretinal surgery in order to remove these tractional membranes. Currently, there are no specific therapeutic agents used for the prevention or treatment of PVR. Pharmacological agents have been tested for the treatment of PVR with different activities including anti-inflammatory, anti-proliferative, anti-neoplastics, and anti-growth factor agents; albeit without reproducible success. (Asaria et al., 2001; Banerjee et al., 2017; Sundaram, Barsam, & Virgili, 2010; Wiedemann, Hilgers, Bauer, & Heimann, 1998) Although some approaches have shown success in early animal models or limited human trials, larger human studies have failed to show a beneficial effect.

A consistency in prior PVR trial design, however, has been that the agents in question were given at the time of surgery only, despite PVR being a disease that manifests 2-3 months later.

[name], observed that intraocular/vitreoretinal lymphoma suspect patients who underwent diagnostic chorioretinal biopsy did not develop epiretinal membranes or PVR when intravitreal methotrexate therapy was used to treat the lymphoma.

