## **6.11. Investigational Product Intravitreal Injection**

Upon completion of the PPV, subjects who are enrolled in the Interventional cohort will receive ADX-2191 400 µg/0.05 mL intravitreal injection, in accordance with the schedule of events (Table 1). The first injection will be administered intraoperatively on Day 0 (V2) or on post-operative Day 1 (V3) and subsequently will be injected on at post-operative Weeks 1 (V4), 2 (V5), 3 (V6) 4 (V7), 5 (V8), 6 (V9), 7 (V10), 8 (V11), 10 (V12), 12 (V13), 14 (V14), and 16 (V15).

Intravitreal ADX-2191 injections will be performed aseptically after the topical application or subconjunctival injection of an anesthetic agent and 5% povidone iodine to the conjunctiva. Each patient will receive an intravitreal injection of 400 µg/0.05 mL ADX 2191, 3.0 mm posterior to the limbus with a 30-gauge needle. It is required that subjects lie on their back/or in a reclined sitting position, with face up, for approximately 20 minutes after the injection to promote optimal IP positioning.

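### The primary test removes first-week re-detachments and unobserved outcomes, but nothing ties the historical rate to the same first-week rule, and no sensitivity analysis for either choice is described

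*Combined protocol and SAP*

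**What the plan says.** Section 9.4.5 decides the primary endpoint on one comparison. It is met "if the upper bound of the confidence interval is lower than the weighted average historical control detachment rate". Section 9.4.1 describes that rate as "a weighted average of the retinal re-detachment rates from two prior Grade C PVR prospective clinical trials with similar inclusion criteria". It gives no value, no weights and no account of how either source trial handled early failures.

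Three rules determine which eyes enter the drug-side proportion.

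- **First-week failures.** Under Section 2.2.1, subjects who re-detach within one week of surgery "will be deemed to have failed Day 0 (day of surgery) and will be removed from the efficacy analysis". Sections 4.3, 4.4, 9.1.1 and 9.4.5 repeat this. The rule reaches dosed eyes, because Section 6.11 places the first injection on Day 0 or Day 1.
- **Missing outcomes.** Section 9.4.5 says: "The primary efficacy analyses will be conducted on the ITT population with observed data only". Section 9.4.2 rules out imputation of detachment data. Section 4.4 anticipates drop-out of up to 20%.
- **Exits before dosing.** Section 4.4 makes these screen failures, outside the analysis.

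On early treatment discontinuation, Section 3.7 has the subject complete the end-of-study (Week 24) visit at that moment, then asks for every effort to retain subjects to Week 24. Section 4.4 follows dosed subjects for safety over the full schedule. Section 6.9 follows subjects who need re-operation for detachment through Week 24. Section 7 requires Week 24 to be at least 24 weeks after surgery, with a two-week tolerance. Section 9.4.5 only encourages discontinuers to stay for the remaining safety assessments.

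**The concern.** In a randomised comparison, a rule that drops early failures applies to both arms, so both rates are counted in the same way. Here the comparator is a fixed number from other trials. If that number counts first-week failures and the trial does not, the difference goes straight into the pass rule and favours the drug. Likewise, an observed-data proportion describes all treated eyes only if the unobserved eyes would have fared like the observed ones. With up to a fifth of eyes possibly unobserved, a reader needs to know how far the conclusion depends on that.

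The secondary comparison with standard of care (Synopsis and Section 9.4.6) applies the first-week removal to both arms and is useful context. It does not protect the primary test, which is passed or failed against the historical number alone.

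**Working it through.** **Inputs from the documents.** Planning rates are 0.2 (drug) and 0.5 (standard of care), with 45 per group and about 80% power (Section 9.3.1). The test is two-sided at 0.05 with a 95% interval (Sections 9.4.1, 9.4.5). Drop-out is up to 20% (Section 4.4). The Synopsis plans about 100 evaluable eyes, 50 per treatment. Part 1a randomised some eyes to Control, so the number of drug-treated eyes is not fixed.

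**Assumptions.** Exact (Clopper–Pearson) limits are used, since no interval method is named. Historical rates h are 0.3, 0.4 and 0.5; Section 1.1 cites anatomic success of 45–80%, that is, failure of 20–55%. Analysed eyes n are 50, 75 and 100. First-week rates r are 2% and 5%.

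**The plan's own figure.** For 0.2 against 0.5, the uncorrected size is [1.96·√(2·0.35·0.65) + 0.8416·√(0.16 + 0.25)]² / 0.3² = 38.5. The continuity correction gives (38.5/4)·[1 + √(1 + 4/(38.5·0.3))]² = 44.9, so 45 per group; power at 45 is 80.1%. The stated figure reproduces. It belongs to the two-arm design used before Version 5.0 and does not size the present rule.

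**Step 1: first-week removal on the trial side only.** The largest passing counts against h = 0.3 / 0.4 / 0.5 are 8 / 12 / 17 for n = 50, 14 / 21 / 28 for n = 75, and 20 / 30 / 39 for n = 100. With no drug effect and a true rate of h including first-week failures, the rate among analysed eyes is (h − r)/(1 − r). At r = 0.05 this gives 0.263, 0.368 and 0.474. The chance of passing is the binomial probability of at most the passing count:

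| n analysed | r = 0 (h = 0.3 / 0.4 / 0.5) | r = 2% | r = 5% |
|---|---|---|---|
| 50 | 1.8 / 1.3 / 1.6% | 3.0 / 2.0 / 2.3% | 6.2 / 3.8 / 3.9% |
| 75 | 1.9 / 2.1 / 1.9% | 3.4 / 3.4 / 2.8% | 8.1 / 6.9 / 5.1% |
| 100 | 1.7 / 2.5 / 1.8% | 3.4 / 4.3 / 2.9% | 9.1 / 9.3 / 5.7% |

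Fixing the number of dosed rather than analysed eyes gives similar values at r = 5%: 4.1–5.4% for 50 dosed and 6.1–9.3% for 100 dosed. If the historical rate applies the same removal, this source adds nothing and the r = 0 column holds.

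**Step 2: first-week events at the planning rate.** The upper limit for 20/100 is 0.292. Restoring five first-week failures gives 25/105, limit 0.331. For 10/50 the limit is 0.337; restoring three gives 13/53, limit 0.383.

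**Step 3: all lost eyes as failures.** If 20% of dosed eyes are not analysed, 100 analysed implies 100/0.8 = 125 dosed (25 lost), and 50 implies 50/0.8 = 62.5, rounded up to 63 (13 lost). The lost eyes pool first-week removals and unknown outcomes. Counting all as failures gives (20 + 25)/125 = 45/125, limit 0.451, and (10 + 13)/63 = 23/63, limit 0.496. Both are below 0.5.

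**Step 4: tipping point against an assumed 0.40.** With 125 dosed, 38/125 has limit 0.393 (pass) and 39/125 has 0.401 (fail), so the result reverses at 39 − 20 = 19 of 25 lost eyes. With 63 dosed, 17/63 has 0.397 (pass) and 18/63 has 0.414 (fail), so it reverses at 18 − 10 = 8 of 13.

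**The case against.** The first-week rule is pre-specified, consistently stated and clinically reasoned. Section 1.1 notes that earlier agents were given only at surgery "despite PVR being a disease that manifests 2-3 months later", so a detachment within days points to the operation. Eligibility also requires complete reattachment at the end of surgery, which makes the removal resemble an eligibility condition. The source trials are said to have similar inclusion criteria. All of this supports keeping the rule, but none of it says what the historical numerator contains.

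A reader might infer that the primary test is biased. The documents do not show this: bias from this source requires that the historical rate counts first-week failures, and they are silent on that. The figures in Step 1 are scenarios, not estimates.

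A reader might also infer from Section 3.7 that an event-free image at an early exit will count as a success. The documents point the other way. Section 3.1 ties evaluable eyes to completing 24 weeks, Section 7 sets a Week 24 window and Section 9.4.2 bars imputation, so such an eye is most naturally missing. What remains is that no section says so, and that the follow-up passages pull in different directions.

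Finally, Sections 9.4.1 and 9.4.9 defer to an SAP to be finalised before database lock, and no separate SAP text is available here. One therefore cannot say that sensitivity analyses will be absent, only that none is described. That SAP is the natural place for them.

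**Conclusion.** The point holds as an inexpensive improvement, not as a demonstrated error. The plan's counting rules are clear, but their effect on a pass or fail against a fixed external number is neither matched on the historical side nor tested.

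If there is a mismatch, 5% one-sided removal takes the false-pass chance from at most 2.5% to between 3.8% and 9.3% over the historical rates and sample sizes considered; with matched rules it stays at most 2.5%. A reader might conclude that 20% loss alone makes a pass untrustworthy. The arithmetic does not support that at the planning rates, where a pass against 0.5 survives even when all lost eyes are failures. Against an assumed 0.40, reversal needs 76% (19/25) or 62% (8/13) of lost eyes to fail when the observed rate is 20%. Fragility is mainly a risk when the observed bound lies near the historical rate, and without that rate the reader cannot tell which case applies.

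These figures rest on exact limits, on the assumed historical and first-week rates, and on 50 to 100 analysed eyes.

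**What to change.** 1. Derive the historical rate with the same first-week rule and 24-week window, or state that the source trials do not allow it.
2. Keep the primary rule. Pre-specify a sensitivity analysis of all dosed Intervention eyes that counts first-week detachments as failures. Restricting it to dosed eyes agrees with Section 4.4.
3. Pre-specify missing-as-failure and tipping-point analyses for dosed eyes without a 24-week outcome. Write down that an event-free image before the Section 7 window is a missing 24-week outcome, as Sections 3.1, 7 and 9.4.2 imply.
4. Reconcile Section 3.7 with Sections 4.4, 6.9, 7 and 9.4.5 on follow-up after early treatment discontinuation.

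The cost is protocol and SAP wording and modest extra analysis. No new visits are needed, and the primary estimate and pass rule keep their form. The downside is that the supporting rates may look less favourable than the primary one, and that matching the historical rate may prove impossible.
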